3.3.2 Periods

Pre-treatment period

The pre-treatment period starts at the date of signed informed consent and ends before the date and timepoint of first dose of Investigational Product (IP).

On-treatment period

The on-treatment period will be calculated from the date and timepoint (as in time of day) of the first dose of IP to the earliest of date of last dose, date of withdrawal of consent or date of death. If withdrawal of consent or death did not occur, it will be calculated from the time of the first dose of IP to the earliest of date of last dose of study drug or the last study visit. If the timepoint of first dose of IP is missing, only the day of first dose of IP will be used.

Follow-up period

The follow-up period will be calculated from the date of last dose of IP + 1 day to the date of last visit.

3.3.3 Visit Window

For COPDCompEx and the exacerbation related analyses no analysis visit windows will be applied.

For PK related analyses no analysis visit windows will be applied and the actual visits/time points will be used instead.

With the exception of the above, visit windows will be used for all scheduled assessments to allow for by-visit analyses, since not all assessments are performed on the scheduled day. Unless specified otherwise, all efficacy and safety analyses will be based on the analysis visit windows. The actual assessment day will be mapped to the planned study visit following the analysis visit windowing rules below:

- If screening and re-screening visits have same date and time then the re-screening assessment will be used in the analysis.
- If more than one assessment falls within a visit window, the closest non-missing assessment to the scheduled day will be used in the analysis.
- If more than one non-missing assessment actual dates are equidistant from the target day, the earlier assessment will be used in the analysis.

Table 1 Analysis visit windows for CAT and EXACT

Protocol Visit	Week	Analysis Visit	Scheduled Study Day	Visit Window for Analysis (Days)
SV1	Week -4	Screening	-28	All assessments up to and including Day -1
SV3	Week 1	Day 1 Pre-dose	1	All assessments on Day 1prior to the first administration of investigational product

Protocol Visit	Week	Analysis Visit	Scheduled Study Day	Visit Window for Analysis (Days)
SV5	Week 12	Week 12	84	All assessments on or after the first administration of investigational product to 127
SV7	Week 24	Week 24	168	≥128

SV = Study Visit.

Table 2 Analysis visit windows for serum chemistry, haematology, vital signs

Analysis visit windows for serum chemistry, haematology, vita				naematology, vital signs
Protocol Visit	Week	Analysis Visit	Scheduled Study Day	Visit Window for Analysis (Days)
SV1	Week -4	Screening	-28	All assessments up to and including Day -1
SV3	Week 1	Day 1 Pre-dose	1	All assessments on Day 1 prior to the first administration of investigational product
SV4	Week 4	Week 4	28	All assessments on or after the first administration of investigational product to 56
SV5	Week 12	Week 12	84	57 to 127
SV7*	Week 24	EOT [a]	• For completed participant who performed Week 24: 168 For completed participant who performed Week 12 only: 84	• For completed participant who performed Week 24: 128 to 176 For completed participant who performed Week 12 only: 57 to 127
SV8 [†]	End of safety period	14 days post treatment		Treatment end date + 14 (+/-3) days

[[]a] EOT may occur from Week 12 onwards.

Which means that the Week 12 assessment may need to be duplicated for EOT using the Penultimate Observation Carried Forward Imputation Technique, ensuring EOT assessment will also contribute to the Week 12 summary statistics

For vital signs, the analysis visit will be "Day 1" for the post-dose assessment done the day of the first administration.

^{*}If a subject's visit is marked with EOT it is automatically allocated to Protocol Visit SV7. If a subject's SV5 occurs after End of Enrolment, then this visit is also duplicated as SV7.

 $[\]dagger$ If a subject's visit is marked as '14 days post treatment', it is automatically allocated to Protocol Visit SV8 SV = Study Visit.

Table 3 Analysis visit windows for exploratory biomarkers (blood) and clinic spirometry (post-BD)

Protocol Visit	Week	Analysis Visit	Scheduled Study Day	Visit Window for Analysis (Days)
SV1	Week -4	Screening	-28	All assessments up to and including Day -1
SV3	Week 1	Day 1 Pre-dose	1	All assessments on Day 1 prior to the first administration of investigational product
SV4	Week 4	Week 4	28	All assessments on or after the first administration of investigational product to 56
SV5	Week 12	Week 12	84	57 to 127
SV7	Week 24	Week 24	168	≥128

BD = Bronchodilator; SV = Study Visit.

For Spirometry assessment at screening, the maximum reading from each series will be used in the analysis. For subjects who have two series of Spiroload screening data, the maximum reading from the latter series will be used for analysis.

Table 4 Analysis visit windows for Thyroid test

able 4 Analysis visit windows for 1 hyroid test				
Protocol Visit	Week	Analysis Visit	Scheduled Study Day	Visit Window for Analysis (Days)
SV1	Week -4	Screening	-28	All assessments up to and including Day -1
SV3	Week 1	Day 1 Pre-dose	1	All assessments on Day 1 prior to the first administration of investigational product
SV5	Week 12	Week 12	84	All assessments on or after the first administration of investigational product to 127
SV7*	Week 24	EOT[a]	For completed participant who performed Week 24: 168 For completed participant who performed Week 12 only: 84	For completed participant who performed Week 24: 128 to 176 For completed participant who performed Week 12 only: all assessments on or after the first administration of investigational product to 127

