1.3 Schedule of Activities

 Table 1
 Schedule of Activities

Procedure	(up to	ening 28 days Day 1)		Inter	vention P	Period		Follow-up Period	Notes	Details in protocol section or appendix
Visit	SV1	SV2	SV3	SV4	SV5	SV6 (VV) ^a	SV7/ EDV ^b	SV8	Study procedures should take place prior to dosing, unless specified otherwise.	
Weeks	-4	-2	1	4	12	18	24	+ 2 post- SV7/EDV	Participants discontinuing study intervention before SV7 should attend the site for SV7 assessments as soon as possible as an EDV. See Section 7.1.4 for details of study end when the last participant has completed 12 weeks of treatment. Visits SV2, SV4, SV7/EDV, and SV8 are visits with a reduced number of assessments. SV6 is a virtual visit.	
Visit Day (window) (days)	-28 to -14	-16 to -14	1	28 (± 3)	84 (± 3)	126 (± 3)	168 (± 3)	+ 14 post- SV7/EDV (± 3)	All Day 1 (SV3) assessments must be collected pre-dose unless otherwise stated. SV1 assessments may occur at any time during screening, including SV2, all must occur within the screening window. Informed consent must be obtained before any study procedure.	
Written informed consent/assignment of E-code	X								Informed consent can be taken prior to SV1.	Appendix A 3
Written informed consent for future use and/or genetic	X									Appendix D
Written informed consent for Cough substudy	X								Required only for participants of the cough substudy.	
Written informed consent for the Q-SAW substudy	-		X	_	—				Required only for participants of the Q-SAW substudy at selected sites. Consent can be obtained any time up until SV5.	Appendix L

Procedure	(up to	ening 28 days Day 1)		Inter	vention P	eriod		Follow-up Period	Notes	Details in protocol section or appendix
Visit	SV1	SV2	SV3	SV4	SV5	SV6 (VV) ^a	SV7/ EDV ^b	SV8	Study procedures should take place prior to dosing, unless specified otherwise.	
Weeks	-4	-2	1	4	12	18	24	+ 2 post- SV7/EDV	Participants discontinuing study intervention before SV7 should attend the site for SV7 assessments as soon as possible as an EDV. See Section 7.1.4 for details of study end when the last participant has completed 12 weeks of treatment. Visits SV2, SV4, SV7/EDV, and SV8 are visits with a reduced number of assessments. SV6 is a virtual visit.	

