2.3.1 Risk Assessment

Identified and potential risks of mitiperstat (AZD4831), along with mitigation strategies, are shown in Table 2.

Table 2Risk Assessment

Potential or identified risk of clinical significance	Summary of data/rationale for risk	Mitigation strategy						
Study intervention Mitiperstat (AZD4831)								
Identified risk								
Maculopapular rash	Generalised maculopapular rash has been observed in healthy volunteers in completed global SAD/MAD studies at single doses of 45 mg and above and at repeated doses of 15 mg and above, at 7 to 10 days post dose. In an MAD study in healthy Japanese and Chinese participants, maculopapular rash CTCAE Grade 1 has been reported in one PPD participant (of 6) on 5 mg mitiperstat (AZD4831); maculopapular rash Grade 2 in 3 PPD participants (of 6) on 10 mg mitiperstat (AZD4831), and maculopapular rash Grade 2 in 1 PPD participant (of 6) on 5 mg mitiperstat (AZD4831). One of 27 patients in the HfpEF study had generalised maculopapular rash CTCAE Grade 3 at 5 mg mitiperstat (AZD4831) occurring 5 days after uptitration from 2.5 to 5 mg.	The DRC will evaluate all cases of skin reaction/rash. The protocol clearly states the actions that have to be taken by the investigator, in case of maculopapular rash (see Appendix B, B 5).						

Table 2Risk Assessment

Potential or identified risk of clinical significance	Summary of data/rationale for risk	Mitigation strategy
Potential risks		

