SV5	Week 12	Week 12	84	All assessments before the administration of investigational product from Day 81-Day 87

 $\overline{SV} = Study Visit.$

Daily assessments from eDiary (PEF, BCSS, cough VAS) will primarily be summarised and analysed as 2-weekly averages, separately. The assessment period of visit windows will be defined in Table 8.

Table 8 Labelling of 2-weekly periods for daily PEF, BCSS, cough VAS

2-weekly period	Adjusted defined windows visit	Scheduled day
Baseline: as defined in Section 3.3.1.1	Baseline	1
Period 1: Evening of Day 1 – Morning of Day 15	Week 2	15
Period 2: Evening of Day 15 – Morning of Day 29	Week 4	29
Period 3: Evening of Day 29 – Morning of Day 43	Week 6	43
Period 4: Evening of Day 43 – Morning of Day 57	Week 8	57
Period 5: Evening of Day 57 – Morning of Day 71	Week 10	71
Period 6: Evening of Day 71 – Morning of Day 85	Week 12	85
Period 7: Evening of Day 85 – Morning of Day 99	Week 14	99
Period 8: Evening of Day 99 – Morning of Day 113	Week 16	113
Period 9: Evening of Day 113 – Morning of Day 127	Week 18	127
Period 10: Evening of Day 127 – Morning of Day 141	Week 20	141
Period 11: Evening of Day 141 – Morning of Day 155	Week 22	155
Period 12: Evening of Day 155 – Morning of Day 172*	Week 24	169

^{*}the 2-weekly period for Period 12 is extended to "Morning of Day 172", to allow for the +3 day window.

The Early Discontinuation and unscheduled visits will be included when applying the visit windows to ensure that all available data are used in the analysis.

For 2-weekly summaries, the mean of all non-missing observations within an assigned window is calculated. If there are fewer than 7 completed days in the 14 day period (where a complete day = entry from the evening AND the following morning) then the analysis value will be set to missing.

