3.3.4 Handling of Unscheduled Visits

Any data collected at early discontinuation and unscheduled visits will be listed and included in the definition of maximum/minimum value. The Early Discontinuation and Unscheduled visits will be included when applying the visit windows to ensure that all available data are used in the analysis.

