3.4.3 Mixed Model Repeated Measures (MMRM)

The MMRM model will be used to fit change from baseline for continuous endpoints that have data at several post-baseline visits. The model will include all available data from all visits, irrespective of whether the patient discontinued study intervention. Since a repeated measures model is being applied, no imputation will be made for missing data. Region will be added as a random effect. The model will include fixed effects for baseline, visit, study intervention and the baseline by visit and study intervention by visit interactions. An unstructured covariance matrix will be used to describe the correlations on a patient between visits, and the Kenward-Roger correction will be used for degree of freedom approximation in the generation of the model. In the event that the model with unstructured covariance matrix fails to converge, an alternative such as autoregressive or compound symmetry will be used instead. Estimates of the least square (LS) mean change from baseline for each study intervention, and the difference between them (AZD4831-placebo), together with two-sided 90% CI, will be obtained from the model for each visit. The study intervention effect will be tested at the 10% two-sided level of significance.

The reportable results from the model are:

- The LSmeans change from baseline at each visit and their standard errors for each study intervention group.
- The difference in change from baseline at each visit between AZD4831 and placebo (LSmeans difference) together with its two-sided 90% confidence interval (CI).
- The two-sided p-value for the difference in change from baseline at each visit between AZD4831 and placebo.

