4.2.1.3 Handling of Dropouts and Missing Data

The "while on treatment" strategy will be used for the primary estimand: if an intercurrent event occurs before first COPDCompEx event, the patient will be censored at the time of intercurrent event.

For participants who do not experience an on-treatment COPDCompEx event,

• If intercurrent event is earlier than date of last dose or the last eDiary date, the participant will be censored at intercurrent event date.

• If the intercurrent event is after the last eDiary date, but earlier than date of last dose, participants who do not experience an on-treatment COPDCompEx event, date of censoring will be last day of eDiary recording.

Intercurrent events are events occurring after treatment initiation (eg, premature treatment discontinuation, switching treatment, terminal events such as death) that affect either the measurement or interpretation of the summary measure (eg, hazard ratio) associated with the clinical question of interest. This study contains 2 intercurrent events:

- 1. Treatment discontinuation (with the following reasons: SAE, death not due to exacerbation, COVID-19, pneumonia, other).
- 2. Prohibited medication.

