4.2.4.3 Handling of Dropouts

The 'while-on treatment' strategy will be used: which means that if an intercurrent event occurs all subsequent data for that participant are excluded from the evaluation.

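### SAP Table 1 gives the CAT and EXACT Week 12 window no lower bound, so an early-discontinuation score can be analysed as a Week 12 result

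*SAP*

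**What the plan says.** **Window.** SAP 3.3.3, Table 1 (CAT and EXACT) gives the Week 12 analysis visit, target Day 84, this range: "All assessments on or after the first administration of investigational product to 127". Week 24 takes everything from Day 128. There is no earlier post-baseline analysis visit. If several scores fall in one window, the one nearest the target is used.

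**Early-discontinuation visits.** The same section says: "The Early Discontinuation and unscheduled visits will be included when applying the visit windows". SAP 3.3.4 repeats this and adds: "Any data collected at early discontinuation and unscheduled visits will be listed and included in the definition of maximum/minimum value".

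**Collection.** Protocol 1.3 says: "Participants discontinuing study intervention before SV7 should attend the site for SV7 assessments as soon as possible as an EDV". The Schedule of Activities marks CAT and EXACT at SV3, SV5 and SV7/EDV only.

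**Exclusion rule.** For EXACT, SAP 4.2.4.3 applies the while-on-treatment strategy: "if an intercurrent event occurs all subsequent data for that participant are excluded from the evaluation". SAP 4.2.7.3 has the same rule for CAT. The intercurrent events, listed in SAP 4.2.1.3, include "Treatment discontinuation (with the following reasons: SAE, death not due to exacerbation, COVID-19, pneumonia, other". Because the list ends in a residual category, I read it as covering any reason for stopping.

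**Model.** SAP 4.2.4.4 and 4.2.7.4 send both endpoints to the MMRM of SAP 3.4.3, which says: "The model will include all available data from all visits, irrespective of whether the patient discontinued study intervention".

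**The concern.** A score taken a few days after first dose says little about the effect at Week 12. If it carries the Week 12 label, it enters the Week 12 mean change for EXACT and CAT. It can also decide whether a participant is counted as having a CAT change of -2 or less, which SAP 4.2.7.4 reports as a simple number and percentage. One SAP rule appears to keep such scores out and another appears to let them in, and the plan does not say which prevails. Two programmers could therefore build different Week 12 datasets from the same text.

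**Working it through.** The plan gives no sample size or rate for CAT or EXACT (Protocol 9.2 covers only the primary endpoint), so there is no stated figure to reproduce. The check traces the rules.

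**Step 1: map study days through the windows.** Table 3 covers clinic spirometry.

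| Study day | Table 1 (CAT, EXACT) | Table 3 (spirometry) | Days before Day 84 |
|---|---|---|---|
| 10 | Week 12 | Week 4 | 84 - 10 = 74 |
| 28 | Week 12 | Week 4 | 84 - 28 = 56 |
| 56 | Week 12 | Week 4 | 84 - 56 = 28 |
| 57 | Week 12 | Week 12 | 84 - 57 = 27 |

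**Step 2: could a later score displace the early one?** Usually not. CAT and EXACT are not collected between SV3 and SV5 except at an EDV, and not at SV8. For someone who stops early, the EDV score is normally the only post-baseline value, so the nearest-to-target rule has nothing to choose from.

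**Step 3: does the while-on-treatment rule remove it?** SAP 3.3.2 runs the on-treatment period to the date of last dose and starts follow-up the next day. The SAP does not say whether a discontinuation is dated at the last dose or at the decision to stop. That gives three cases:

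- *EDV after drug was stopped.* SAP 4.2.4.3 and 4.2.7.3 exclude the score; SAP 3.4.3 read literally keeps it.
- *EDV on the day of last dose.* SAP 3.3.2 counts that day as on treatment, so the score is not clearly subsequent to the event.
- *EDV at study withdrawal.* Protocol 7.2 holds the EDV, if possible, at the time of withdrawal, with study drug stopped at that point. If the last tablet was taken the day before, the score is in follow-up when the event is dated at last dose, but not after the event when it is dated at the decision to stop.

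**Step 4: would a lower bound work?** A Day 57 start leaves Day 10 outside Week 12. So does a midpoint rule: (1 + 84)/2 = 42.5, giving a start at Day 43.

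**The case against.** The best defence is that the endpoint-specific rule governs. Every planned CAT and EXACT table in SAP Appendix B (14.2.2.5 to 14.2.2.9) is labelled while on treatment, and no treatment-policy version exists for them. SAP 3.4.3 is a general methods section that also serves treatment-policy analyses of FEV1 and other spirometry. A similar sentence sits in SAP 3.4.4, although both rate endpoints are while on treatment, so it reads like template text. Most of this stands: the natural reading is that an EDV held after stopping drops out. The SAP does not say so, however, and the same-day and withdrawal cases remain open even on that reading.

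A second defence is that Table 3 starts Week 12 at Day 57 because spirometry has a Week 4 visit, which CAT and EXACT lack. Tables 4 and 6 have the same open start, so the choice looks deliberate, to use all available data. That is fair, and Day 57 is not the only reasonable bound. It does not make a score 74 days before target a Week 12 measurement.

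A reader might go further and infer that drug rash loads the active arm with early scores. Protocol 4.3 reports rash at 5 mg in 1 of 27 participants in the heart-failure study and in 1 of 6 and 1 of 6 in the Japanese and Chinese study. Taking the latter as separate groups, 1/27, 3/39 pooled and 2/12 give 3.7%, 7.7% and 16.7%, or about 8, 16 and 34 of 203. If all those scores entered and showed none of the effect, the Week 12 difference would be 1 - p of its full value: about 96%, 92% or 83%. The documents do not support that as a finding:

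- Protocol 7.1.2 tells participants with a rash to stop drug and then call, and Protocol 8.4.9 describes an additional visit before any EDV. Most rash EDVs therefore follow the event and are excluded.
- The timing in Protocol 2.3.1 was seen "at single doses of 45 mg and above and at repeated doses of 15 mg and above, at 7 to 10 days post dose". Protocol 4.3 is more general but concerns healthy subjects. The 1 of 27 case arose 5 days after uptitration to 5 mg.
- No placebo rate and no rate in COPD is given, and early stops for other reasons could occur in either arm.

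**Conclusion.** The gap is real but narrow. Table 1 allows a CAT or EXACT score from any day after first dose to stand as Week 12. The while-on-treatment rule probably closes most of the gap, including most rash EDVs. It does not clearly cover EDVs on the day of last dose or at study withdrawal, and SAP 3.4.3 contradicts it.

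The number of participants affected and any difference between arms cannot be derived from the documents. If the exclusion is applied strictly and the event is dated at the last dose, only same-day scores remain in question and the effect may be close to nil. If SAP 3.4.3 prevails, every early EDV score counts as Week 12. The exposed results are the Week 12 mean changes in EXACT and CAT and the CAT proportion. The primary endpoint uses no visit windows (SAP 3.3.3) and is not affected.

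**What to change.** 1. In Table 1, start the Week 12 window at Day 57, as in Table 3, and list earlier post-dose CAT and EXACT scores without assigning them to a visit. A Day 43 start would also serve.
2. State that, for while-on-treatment analyses, the intercurrent-event exclusion is applied before windowing and overrides the SAP 3.4.3 sentence on data after discontinuation. The bound alone is not enough: under SAP 3.4.3, an EDV on Day 60 after stopping on Day 58 would still count as Week 12.
3. Define the date of a treatment discontinuation as an intercurrent event, and say how a score from that same day is treated.
4. Add the matching exception to the sentences in SAP 3.3.3 and 3.3.4 that bring EDVs into the windows.

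The cost is one table cell and a few sentences, with no change to data collection. A few early EDV scores leave the CAT and EXACT models. Since SAP 3.4 takes percentages out of the arm total unless stated otherwise, the denominator for the CAT proportion should also be stated, so that it is clear how a participant with no Week 12 score is counted.

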SV5	Week 12	Week 12	84	All assessments before the administration of investigational product from Day 81-Day 87

 $\overline{SV} = Study Visit.$

Daily assessments from eDiary (PEF, BCSS, cough VAS) will primarily be summarised and analysed as 2-weekly averages, separately. The assessment period of visit windows will be defined in Table 8.

Table 8 Labelling of 2-weekly periods for daily PEF, BCSS, cough VAS

2-weekly period	Adjusted defined windows visit	Scheduled day
Baseline: as defined in Section 3.3.1.1	Baseline	1
Period 1: Evening of Day 1 – Morning of Day 15	Week 2	15
Period 2: Evening of Day 15 – Morning of Day 29	Week 4	29
Period 3: Evening of Day 29 – Morning of Day 43	Week 6	43
Period 4: Evening of Day 43 – Morning of Day 57	Week 8	57
Period 5: Evening of Day 57 – Morning of Day 71	Week 10	71
Period 6: Evening of Day 71 – Morning of Day 85	Week 12	85
Period 7: Evening of Day 85 – Morning of Day 99	Week 14	99
Period 8: Evening of Day 99 – Morning of Day 113	Week 16	113
Period 9: Evening of Day 113 – Morning of Day 127	Week 18	127
Period 10: Evening of Day 127 – Morning of Day 141	Week 20	141
Period 11: Evening of Day 141 – Morning of Day 155	Week 22	155
Period 12: Evening of Day 155 – Morning of Day 172*	Week 24	169

^{*}the 2-weekly period for Period 12 is extended to "Morning of Day 172", to allow for the +3 day window.

The Early Discontinuation and unscheduled visits will be included when applying the visit windows to ensure that all available data are used in the analysis.

For 2-weekly summaries, the mean of all non-missing observations within an assigned window is calculated. If there are fewer than 7 completed days in the 14 day period (where a complete day = entry from the evening AND the following morning) then the analysis value will be set to missing.

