4.1.6 Study Conduct Mitigation During SARS-CoV-2 Pandemic

In case of local or global SARS-CoV-2 outbreaks, appropriate risk assessments and mitigation measures will need to be taken into consideration to protect participants and HCPs involved in the clinical study and ensure data quality as per regulatory agencies and local guidelines.

If, for reasons related to the COVID-19 pandemic (eg, local lockdown, self-isolation requirements), a participant is not able to attend their scheduled visit within the visit window, they can have their visit rescheduled as per agreement with the AstraZeneca Study Physician. Where visits cannot be rescheduled, participants should continue at the next scheduled visit. Additionally, on-site visits may be replaced by a telemedicine visit if allowed by local/regional guidelines. Having a telemedicine contact with the participants will allow collection of data for AEs, concomitant medications, adherence to the e-Diary, and PRO measures to be reported and documented. The term telemedicine visit refers to remote contact with the participants using telecommunications technology including phone calls, virtual or video visits, and mobile health devices.

Applicable measures for source data verification, if on-site monitoring at the study sites is not indicated due to the COVID-19 pandemic, should be implemented.

For further details on study conduct during SARS-CoV-2 or similar pandemic refer to Appendix K.

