In cases of 'unconfirmed pneumonia', if the participant is not hospitalised and/or does not have a chest x-ray confirming diagnosis of pneumonia, this should generally be considered an infective exacerbation of COPD rather than pneumonia. In this scenario, study intervention can continue. If the investigator still considers this to be pneumonia, then discussion with the AstraZeneca medical monitor would be needed regarding continuation/discontinuation of study intervention.

In case of serious infection, the study intervention should be immediately discontinued on a temporary basis, unless any permanent discontinuation criteria are met (Section 7.1). After discontinuation of study intervention, any appropriate treatment is allowed if conditions presented in Section 6.9 are met.

Study intervention does not need to be stopped for antibiotic treatment of non-serious infection.

If a participant does not receive study intervention for ≥ 28 days continuously, they should be permanently withdrawn from the study intervention.

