7.1.3 Restarting After Temporary Discontinuation

Participants who have temporarily discontinued study intervention can resume treatment as soon as, in the opinion of the investigator, the participant is able to re-start study treatment and the participant wishes to resume. No minimum time period is necessary before treatment can

resume, with the exception of participants who temporarily discontinued due to COVID-19, pneumonia or serious infection:

- If the study intervention has been temporarily discontinued due to confirmed COVID19 infection, it may be possible to resume the study intervention at least 7 days after the confirmatory rapid screening test or PCR test if, in the opinion of the investigator, the symptoms related to COVID19 were mild and have resolved.
- If the study intervention has been temporarily discontinued due to confirmed pneumonia or serious infection, it may be possible to resume the study intervention at least 7 days after completion of anti-microbial therapy if, in the opinion of the investigator, the symptoms related to pneumonia or serious infection were not severe and have resolved.

If the participant misses a scheduled visit during temporary discontinuation of study intervention, the missed visit should be recorded as "not done", unless:

- SV5 is missed, in which case it should be performed as soon as possible (eg, when the investigator believes an episode of serious infection, pneumonia or COVID19 has resolved).
- SV7 is missed, in which case it should be performed as soon as possible (eg, when the investigator believes an episode of serious infection, pneumonia or COVID-19 has resolved). The participant should not be re-dosed, but should complete all assessments as per the visit and continue in follow-up (this will ensure data are available at SV7 for the analysis).

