8.3.2 Vital Signs

Vital signs (supine BP [average of 3 measurements], respiratory rate, pulse rate, and body temperature) will be performed in-clinic at timelines as specified in the SoA (Table 1).

Vital sign assessments are to be collected using equipment supplied by the investigator.

At Visits SV3 and SV5, the vital signs BP measurements can be used for the pre-dose supine measurements for the orthostatic test, if taken after being supine for at least 10 minutes and as long as the standing BP measurements are taken after these supine measurements at the time intervals described below for the orthostatic blood pressure measurement.

The measurements should be done before any blood sampling. The measurements should be preceded by at least 5 minutes of rest for the participant in a quiet setting without distractions.

Orthostatic Blood Pressure Measurements and Follow-up of Confirmed Orthostatic Hypotension

Orthostatic BP measurements will be obtained using a standard sphygmomanometer after scheduled supine measurements (1 and 3 minutes after the participant stands) and prior to any required blood draw:

- At SV3 (baseline; Day 1), orthostatic BP should be measured pre-dose and 1 to 2 hours post dose.
- At SV5 (Week 12), orthostatic BP should be measured pre-dose.

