For each visit/timepoint, up to 2 additional orthostatic blood pressure sequences may be performed. For each sequence, the orthostatic hypotension is defined by a decrease (between supine value and values at 1 or 3 minutes after standing) of \geq 20 mmHg for SBP or \geq 10 mmHg for DBP. The orthostatic hypotension for the visit/timepoint is confirmed if 2 of 2 or 2 of 3 sequences have demonstrated hypotension or if symptoms are reported to have occurred at

any of the sequences. When orthostatic hypotension is confirmed, the investigator reports an "Orthostatic Hypotension" adverse event specifying the date and time.

Details about the orthostatic blood pressure assessment are described in Appendix A.

The following definitions will be applied:

- BP decrease: orthostatic hypotension derived from orthostatic BP data with at least 2 positive sequences (ie. 2 of 2 or 2 of 3).
- BP decrease reported as AE: "Orthostatic Hypotension" AE starting the same day on Day 1 Pre-dose, Day 1 Post-dose or within the same day of the 12 weeks measurement.

The three following timepoints will be considered:

- Day 1 pre-dose
- Day 1 post-dose
- Week 12

For BP decrease, the CRF visit/timepoint variables will be used. For BP decreased reported as AE, these timepoints should be derived from exposure dates and times, and "Orthostatic Hypotension" start dates and times.

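### SAP Table 7 and SAP 4.7.6.1 assign the Week 12 orthostatic blood pressure test by different rules, so an SV5 test done after Day 87 is Week 12 under one and unassigned under the other

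*SAP*

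**What the plan says.** **The day-window rule.** SAP 3.3.3, Table 7, gives the Week 12 orthostatic window as "All assessments before the administration of investigational product from Day 81-Day 87". It has no other row after Day 1.

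**The CRF rule.** SAP 4.7.6.1 defines BP decrease as at least two positive sequences and adds: "For BP decrease, the CRF visit/timepoint variables will be used".

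**Which rule has priority.** SAP 3.3.3 says: "Unless specified otherwise, all efficacy and safety analyses will be based on the analysis visit windows". It explains that windows are needed "since not all assessments are performed on the scheduled day".

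**When the test is done.** Protocol 8.3.2 states: "At SV5 (Week 12), orthostatic BP should be measured pre-dose". The Schedule of Activities puts SV5 at Day 84 ± 3. Protocol 7.1.3 says a visit missed during a temporary stop of study drug is recorded as not done, with exceptions that include SV5: "SV5 is missed, in which case it should be performed as soon as possible". For participants kept from a visit by COVID-19, protocol 4.1.6 says "they can have their visit rescheduled as per agreement with the AstraZeneca Study Physician".

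**Where the results go.** Under SAP 4.7.6.2 and Appendix B, Table 14.3.8.5 counts participants with BP decrease, and with BP decrease reported as an adverse event, by timepoint. Table 14.3.8.6 lists participants with at least one positive sequence and gives the number of positive sequences at Day 1 pre-dose, Day 1 post-dose and Week 12.

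**The concern.** The two rules agree for every SV5 held on Day 81 to 87 and disagree for every one held outside it. Two programmers could each follow the SAP and produce different Week 12 results.

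Table 7 is also out of line with its neighbours. Week 12 runs from Day 57 to 127 for vital signs (SAP Table 2) and takes in any assessment after the first dose for ECG (SAP Table 6). Table 7 instead repeats the protocol's visit window, which defeats the reason 3.3.3 gives for having analysis windows.

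SV5 is the only scheduled orthostatic test after Day 1. Blood pressure reduction is a potential risk in protocol 2.3.1, with orthostatic monitoring as part of its mitigation. The late tests are not a random subset: protocol 7.1.3 gives serious infection, pneumonia and COVID-19 as examples of what delays SV5. Infection is itself a listed potential risk of the drug, so delays could differ between arms.

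**Working it through.** **1. Where the Table 7 window comes from.** Protocol SV5 is Day 84 ± 3: 84 − 3 = 81 and 84 + 3 = 87. This is exactly Table 7. Its width is 87 − 81 + 1 = 7 days. The Week 12 window for other vital signs is 127 − 57 + 1 = 71 days.

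**2. How late a legitimate SV5 can be.** Protocol 7.1.3 sets no upper day for a make-up SV5. Protocol 7.1.2 limits the interruption: "If a participant does not receive study intervention for ≥ 28 days continuously, they should be permanently withdrawn from the study intervention". The longest interruption that still permits a restart is therefore 27 days, and the latest restart day is the first day off drug plus 27.

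| First day off drug | Latest restart day | Within Day 81–87 (SAP Table 7)? | Within Day 57–127 (SAP Table 2)? |
|---|---|---|---|
| 60 | 60 + 27 = 87 | yes | yes |
| 70 | 70 + 27 = 97 | no | yes |
| 81 | 81 + 27 = 108 | no | yes |
| 84 | 84 + 27 = 111 | no | yes |
| 87 | 87 + 27 = 114 | no | yes |

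These are restart days, used only to show the range of dates. The visit itself may come before the restart.

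**3. One late visit under each rule.** Take an SV5 on Day 95, recorded as SV5 in the CRF.

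| Item from that visit | Governing text | Timepoint |
|---|---|---|
| Routine vital signs | SAP Table 2 | Week 12 |
| Orthostatic test, day-window rule | SAP Table 7 | none |
| BP decrease (two or more positive sequences) | SAP 4.7.6.1 | Week 12 |
| One positive sequence only (Table 14.3.8.6) | Table 7; 4.7.6.1 does not name it | none, if Table 7 is applied |

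The last row matters because protocol Table 5 does not require a repeat when the drop comes with symptoms. A symptomatic participant may have a single positive sequence, and so fall outside BP decrease but inside Table 14.3.8.6.

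**4. The adverse event row of Table 14.3.8.5.** SAP 4.7.6.1 ties it to the day of the Week 12 measurement without giving a day range. It matches the derived row only if both take that measurement to be the same visit.

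**5. How many participants.** The documents do not give the distribution of SV5 dates. Assuming a share *p* of the 406 planned participants has a late SV5, the number is 406 × *p*: 4.1 at 1%, 12.2 at 3%, 20.3 at 5% and 40.6 at 10%.

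**The case against.** A reader might infer that the plan throws away late orthostatic tests outright. The documents do not support that. Windows in SAP 3.3.3 apply unless another rule is specified, and 4.7.6.1 specifies one for BP decrease. On that reading a late SV5 counts as Week 12 in the derived row of Table 14.3.8.5 and nothing is lost there. This part of the objection stands. It does not dispose of the point: Table 7 is also written specifically for orthostatic blood pressure, and the CRF rule names only BP decrease, so the one-positive-sequence output is left to Table 7.

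A reader might also infer a loss of safety information. Even where Table 7 is applied, SAP 4.7.6.2 lists all vital signs. Protocol 8.3.2 requires confirmed orthostatic hypotension, and symptoms related to the test, to be reported as adverse events, and SAP 4.7 analyses these through SV8. What can be lost is an entry in a Week 12 output.

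Nor can the affected tests be called on-treatment without qualification. After pneumonia or serious infection, protocol 7.1.3 allows dosing to resume no sooner than 7 days after anti-microbial therapy ends, whereas SV5 is due as soon as possible. A make-up SV5 can therefore be done off drug.

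Loss of precision is not a valid argument either. The summary is counts and percentages, with no confidence interval planned. Estimates of the number affected that assume a spread of visit days around Day 84 have no source in the documents.

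**Conclusion.** The inconsistency is real and minor. SAP Table 7 and SAP 4.7.6.1 give different timepoints to the same test whenever SV5 falls outside Day 81 to 87, and protocol 7.1.3 and 4.1.6 provide legitimate routes to a date after Day 87. For the BP-decrease row the CRF rule can be read as governing. For the one-positive-sequence output, Table 14.3.8.6, it does not literally apply, and late tests can drop out of Week 12.

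The size is unknown. About 4 to 41 participants is an illustration that rests on an assumed 1% to 10% of 406 with a late SV5, and it treats every randomised participant as reaching SV5. No efficacy result or formal test is affected.

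**What to change.** In SAP Table 7, replace the Day 81 to 87 range for Week 12 with the pre-dose orthostatic test recorded at CRF visit SV5, which matches 4.7.6.1. State that this one definition applies to the derived and adverse-event rows of Table 14.3.8.5 and to Table 14.3.8.6. Flag tests done while study drug was interrupted, so that they can be told apart from tests on drug.

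Borrowing Day 57 to 127 from SAP Table 2 would keep the late tests shown above, but would leave a day window in Table 7 against a CRF rule in 4.7.6.1, so the conflict would remain.

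The cost is one line in an SAP table plus a flag. The downside is that the Week 12 label covers a somewhat wider range of days, as it already does for routine vital signs.
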